	
Three patients ate the whole portion, 3 ate half, and 3 ate less than half of the portion. Patients were also asked at what time of day they would prefer to eat the product. Four patients preferred to eat the product for breakfast, 1 as a mid-afternoon snack, 2 preferred the product in the evening, and 2 patients would eat the product at any time of day. This pilot helped to inform patient facing materials, data collection templates, and gave early indication regarding the palatability of the trial product.
 
To help with further development of ONS flavours, a PPI survey was distributed to 25 older adults (age 86.23 ± 5.93 years; 56% female; 92% White British, 8% Indian) on UHS geriatric medical wards. We assessed patients' likability for porridge and porridge flavours using a 7-point Likert scale from 'definitely like' (7) to 'definitely dislike' (1). Analyses showed a median likability rating of 5 'mildly like' (IQR 3-6) for porridge with 60% circling a score in the 'like' section of the scale, 8% neither like nor dislike, and 32% circling scores in the 'dislike' section. Three participants explained they have difficulty swallowing, so even though porridge was not their favourite snack they would eat it as they can only manage soft foods. When asked 'what is your favourite type of snack to eat between meals?' most preferred fruit (n = 7, 28%), or biscuits (n = 6, 24%), and 16% preferred not to eat any snacks.
 
The top three flavours of porridge that participants were most likely to eat were golden syrup (44% like, 8% neither like nor dislike, 48% dislike), strawberries and cream (32% like, 8% neither like nor dislike, 60% dislike), and apple and cinnamon (32% like, 8% neither like nor dislike, 60% dislike). Participants were asked 'when you make porridge for yourself what flavour do you prefer to eat?' Participants preferred neutral porridge with sugar, strawberry jam, or golden syrup added (n = 18, 72%).
 
1 public contributor provided input into this study proposal. They will be invited to join the study management group and be involved from development to dissemination of study findings.

Dissemination	Results will be shared with commissioning services, NHS staff, and service users, supported by our PPI partners. Results will also be shared via publication and conference presentations.
Planned Study Period	Start Date: 1 st April 2024 End Date: 31 st October 2024 Years: 0 Months: 7 Days: 0

FUNDING AND SUPPORT IN KIND

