Participants will be prescribed ONS twice per day for 4 days, in addition to normal meals, in a crossover design. Two ONS products (Table 1) will be tested for palatability and compliance including a new fortified porridge (treatment), and standard liquid-based ONS (control). Each ONS product will be tested over 2 days in a randomised crossover sequence (Figure 1). The products will be offered twice per day, in-between breakfast and lunch, and after dinner to reduce the detrimental long period of calorie absence experienced overnight [33]. The fortified porridge (treatment) is powdered and mixed with 100 ml boiling water in a carton with a choice of 4 flavours including golden syrup, apple and cinnamon, strawberries and cream, and bananas and custard. The liquid-based ONS (control) are ready-to-drink milkshakes. Participants will be offered the ONS in a screw-topped plastic bottle, and a choice from a variety of flavours (e.g., vanilla, strawberry, chocolate, banana, mocha, neutral, berries). ONS products will be prepared and distributed to participants by health care professionals working on the wards.

Table 1. ONS Product Information (see appendices for full product specification)

Group	Treatment	Control
Name	Vital Daily High Protein Oats (Adams Vital Nutrition Ltd.)	Anonymous readymade drink supplement
Description	Fortified 'build and restore' porridge ONS	Standard liquid-based ONS
Weight (g)	157	125
Energy (kcal)	230	306
Protein (g)	15	18.3

Data Collection

Participant Characteristics

Participant characteristics including age, domicile status, marital status, care provision, usual residence, frailty (PRISMA-7), sarcopenia (SARC-F), and appetite (SNAQ) will be assessed at baseline. Moreover, participants C-reactive protein [34] and National Early Warning Score [35] will be

recorded as markers of acute illness (recorded as part of standard care), a potential mediator of older adults' appetite [36].

Appetite will be measured using the Simplified Nutritional Appetite Questionnaire (SNAQ) [37], which has been validated to predict weight loss in community dwelling older adults and used to predict poor health outcomes in hospitalised older people [37-39]. SNAQ is a four-item tool comprising items 1, 2, 4 and 6 of the CNAQ, assessing appetite, satiety, taste of food and number of meals per day respectively. SNAQ has a maximum score of 20, with a score of ≤ 14 indicating poor appetite.

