Potassium	mg (mmol)	97.6 (2.50)	122 (3.13)
Chloride	mg (mmol)	60.0 (1.69)	75 (2.11)
Calcium	mg (mmol)	350 (8.73)	438 (10.9)
Phosphorus	mg (mmol)	282 (9.11)	353 (11.4)
Magnesium	mg (mmol)	54.0 (2.22)	68 (2.78)
Iron	mg	2.19	2.74
Zinc	mg	2.58	3.23
Copper	mg	0.35	0.44
Manganese	mg	0.64	0.80
Fluoride	mg	0.18	0.23
Molybdenum	μ g	215	26.9
Selenium	μ g	15.4	19.3
Chromium	μ g	13.0	16.3
Iodine	μ g	49.0	61.3

Other nutrient information :

Nutrients	Unit	per 100ml	per 125ml
Choline	mg	99.4	124.3
Water	g	62	78
Osmolarity	mOsmol/l	570	570
Potential renal solute load	mOsmol/l	971	971
pH		6.6	6.6

Adams Vital Nutrition Ltd. Vital Daily High Protein Oats - product specification
 Product Specification

 VITAL DAILY PORRIDGE GF **GOLDEN SYRUP**

Valid in: United Kingdom
 Manufactured in: UK
 General description: Golden Syrup flavour porridge fortified with vitamins and minerals

Product information

suitable for
 vegans contains
 no yeast extract
 high protein
 gluten free

According to regulation 828/2014/EU

Characteristics

Texture: powder
 Texture (after preparation): homogeneous
 Convenience: instant

Preparation			Cooking time: 0 minutes	
Quantity	Ingredient		Temperature	Instruction
57.00 g 100.00 g	product water		-	57g powder to 100ml boiling water. Mix well
Yield ca.: 157.000 g				

Shelf life (provisional)

12 Months

Storage instructions

Keep in a cool and dry place (8-25°C) and protect from light and frost. Always close the container properly.

Nutrition Information		Unit	Typical value per 100g	GDA [%]* typical value per 100g	Per serving per 100g	GDA [%]* per serving per 100g	Per serving per 157g	GDA [%]* per serving per 157g
Energy	kJ	1652			600		941	
	kcal	391	20		142	7	223	11
fat	g	7.8	11.1		2.8	4.0	4.4	6.3
of which:								
- saturates	g	1.6	8.0		0.6	2.9	0.9	4.6
carbohydrate	g	55.8	21.5		20.3	7.8	31.8	12.2
of which:								
- sugars	g	32.7	36.3		11.9	13.2	18.6	20.7
fibre	g	4.5			1.6		2.6	

The RELISH Study

protein	g	21.2	42.4	7.7	15.4	12.1	24.2
salt**	g	0.75	12.51	0.27	4.54	0.43	7.13

**Salt calculated from the sodium content * 2.5

* = % of the daily "reference intake of an average adult (8400 kJ / 2000 kcal)". The nutritional needs of individuals may be higher or lower, based on gender, age, level of physical activity and other factors.

Additional Nutrition Information	Unit	Typical value per 100g	GDA [%]* typical value per 100g	Per serving per 100g	GDA [%]* per serving per 100g	Per serving per 157g	GDA [%]* per serving per 157g
moisture	g	8.0					

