salt (NaCl)	g	0.3		0.1		0.2	
calories out of protein	kcal	85		31		48	
sodium	g	0.30		0.11		0.17	

Health&Nutrition information value	Unit	100% RDA	Typical value per 100g		Per serving per 100g		Per serving per 157g	
			%*	%*	%*	%*		
calcium	mg	800.00	368.98	46.12	133.96	16.74	210.32	26.29
copper	mg	1.00	0.95	94.87	0.34	34.44	0.54	54.07
iodine	µg	150.00	63.00	42.00	22.87	15.25	35.91	23.94
iron	mg	14.00	11.52	82.30	4.18	29.88	6.57	46.91
magnesium	mg	375.00	133.33	35.55	48.41	12.91	76.00	20.27
phosphorus	mg	700.00	363.71	51.96	132.05	18.86	207.31	29.62
potassium	mg	2000.00	194.21	9.71	70.51	3.53	110.70	5.53
selenium	µg	55.00	37.60	68.36	13.65	24.82	21.43	38.97
zinc	mg	10.00	8.99	89.91	3.26	32.64	5.13	51.25
biotin	µg	50.00	33.91	67.82	12.31	24.62	19.33	38.66
folic acid	µg	200.00	235.10	117.55	85.35	42.68	134.01	67.00
niacin	mg	16.00	7.46	46.64	2.71	16.93	4.25	26.59
pantothenic acid	mg	6.00	3.09	51.57	1.12	18.72	1.76	29.39
riboflavin	mg	1.40	0.93	66.40	0.34	24.11	0.53	37.85
thiamin	mg	1.10	1.20	108.68	0.43	39.46	0.68	61.95
vitamin A	µg	800.00	360.00	45.00	130.70	16.34	205.20	25.65
vitamin B12	µg	2.50	1.44	57.60	0.52	20.91	0.82	32.83
vitamin B6	mg	1.40	1.01	72.02	0.37	26.15	0.57	41.05
vitamin C	mg	80.00	108.16	135.20	39.27	49.09	61.65	77.07
vitamin D	µg	5.00	18.00	360.00	6.54	130.70	10.26	205.20
vitamin E	mg	12.00	7.69	64.10	2.79	23.27	4.38	36.54
vitamin K	µg	75.00	46.80	62.40	16.99	22.65	26.68	35.57

* = % recommended daily allowances

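### Table 1 gives a porridge portion 15 g protein and 230 kcal, the only appended porridge specification gives 12.1 g and 223 kcal, and the plan does not say which converts grams eaten into protein and energy intake

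*Combined protocol and SAP*

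**What the plan says.** Section 3 (Intervention) of the combined protocol and SAP describes two products given twice a day, two days each. Its product table is headed "Table 1. ONS Product Information (see appendices for full product specification"). For the porridge it lists 157 g, 230 kcal and 15 g protein. For the liquid control it lists 125 under a weight-in-grams row, 306 kcal and 18.3 g. The protein row reads "Protein (g) 15 18.3". There is one porridge column, although patients get "a choice of 4 flavours including golden syrup, apple and cinnamon, strawberries and cream, and bananas and custard".

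The appended porridge specification is for one flavour, described as "Golden Syrup flavour porridge fortified with vitamins and minerals". Its preparation line is "57g powder to 100ml boiling water. Mix well", with a yield of about 157 g. Its protein row is "protein g 21.2 42.4 7.7 15.4 12.1 24.2": 21.2 g per 100 g powder, 7.7 g per 100 g prepared and 12.1 g per 157 g serving, with reference-intake percentages between them. Energy on the same three bases is 391, 142 and 223 kcal. A further row, "calories out of protein", gives 48 kcal per 157 g serving.

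Under Primary Outcome Measures (Compliance), leftovers are weighed in grams, and mean ONS energy and protein per day are to be calculated. Quantitative data analysis lists both for description. The ONS intake form in the data collection booklet has blank spaces for amount given, amount left, kcal and protein. None of these places states a conversion value or says whether it varies by flavour.

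**The concern.** Table 1 sends the reader to the appendices, and the appendix disagrees with it for the same serving weight. Two analysts with identical leftover weights could therefore report different porridge protein, and a different protein contrast with the liquid, each citing the protocol. Section 2.2 says the study will inform whether the product suits the hospital and wider roll-out, so the protein it delivers will interest readers. Section 1 also cites a minimum of 30 g ONS protein per day. Two full portions give exactly 30 g on Table 1 and 24.2 g on the golden syrup specification.

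The control has a smaller problem of the same kind. Its 125 appears as grams in Table 1, whereas its specification is per 125 ml. A 125 ml bottle of this product does not weigh 125 g, so using 125 as the starting weight against weighed leftovers would be wrong.

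**Working it through.** **Does Table 1 reproduce from the appendices?**

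- Control, from its specification per 100 ml: 14.6 × 1.25 = 18.25 g protein and 245 × 1.25 = 306.25 kcal. Table 1 has 18.3 and 306, so it reproduces.
- Porridge, powder basis (57 g): 21.2 × 0.57 = 12.08 g and 391 × 0.57 = 222.9 kcal.
- Porridge, prepared basis (157 g): 7.7 × 1.57 = 12.09 g and 142 × 1.57 = 222.9 kcal.
- Energy from protein: 48 kcal ÷ 4 kcal/g = 12 g.

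The specification agrees with itself on all three routes. Table 1's 15 g and 230 kcal do not reproduce. A different scoop of powder cannot explain both: 15 g protein would need 15 ÷ 0.212 = 70.8 g of powder, while 230 kcal would need 230 ÷ 3.91 = 58.8 g.

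**Size per golden syrup portion**

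- Protein: 15 ÷ 12.1 = 1.240, so Table 1 is 24% above the specification. In reverse, 12.1 ÷ 15 = 0.807, or 19% below.
- Energy: 230 ÷ 223 = 1.031 and 223 ÷ 230 = 0.970, about 3% either way.

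**Effect on the contrast, if one source applied to every porridge portion (two portions a day)**

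| | Table 1 | Specification |
|---|---|---|
| Porridge protein, full intake | 2 × 15 = 30 g | 2 × 12.1 = 24.2 g |
| Liquid protein, full intake | 2 × 18.3 = 36.6 g | 36.6 g |
| Liquid minus porridge, full intake | 6.6 g/day | 12.4 g/day |
| The same at 67% intake of both | 4.4 g/day | 8.3 g/day |
| Energy gap, full intake | 612 − 460 = 152 kcal | 612 − 446 = 166 kcal |

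The 67% is the hospital mean compliance cited in Section 1, used only as an illustration. At unequal intakes the sign can change. The products deliver equal protein when the fraction of liquid taken, divided by the fraction of porridge taken, is 15 ÷ 18.3 = 0.82 on Table 1 or 12.1 ÷ 18.3 = 0.66 on the specification. Between those ratios the two sources disagree on which product gave more protein.

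**Control weight**

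Listed protein, carbohydrate, fat and water per 100 ml are 14.6 + 25.1 + 9.6 + 62 = 111.3 g, so a 125 ml bottle holds about 111.3 × 1.25 = 139.1 g. The per-125 ml column gives 18.3 + 31.4 + 12 + 78 = 139.7 g. If 125 were entered as amount given while leftovers were weighed, the reading would be 1 − (1 − true) × 139.1/125. A true 67% then reads 1 − 0.33 × 1.113 = 63.3%. A finished bottle reads 100% correctly. An untouched bottle reads −11.3%.

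**The case against.** The strongest reply is that both porridge figures may be right: Table 1 may describe the range or another flavour, and the specification describes golden syrup. The documents do not exclude this. It means Table 1 cannot be called wrong, and 24% and 19% cannot be read as limits on the error in mean porridge protein. A reader might infer such limits, but that requires the other three flavours to lie between 12.1 and 15 g, which is nowhere stated. For example, if 15 g were an equal-weight mean of the four flavours, the other three would average (60 − 12.1) ÷ 3 = 16.0 g. Applying 12.1 g to those would understate them by 1 − 12.1/16.0 = 24%, beyond the 19%.

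Nor can flavour choice be predicted. The survey reports "The top three flavours of porridge that participants were most likely to eat were golden syrup (44% like", but 48% disliked it. In the separate pilot, 8 of 9 patients chose chocolate over golden syrup, and chocolate is not among the four trial flavours.

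It is also fair to say that the mismatch falls on supporting measures. The compliance objective in Section 2.1 is percentage intake, which needs only weights, and palatability needs no composition data. Energy, the nutrient measure in the planned repeated measures ANOVA, moves by about 3% per golden syrup portion.

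On the control, a reader might infer that compliance is biased in favour of porridge. The documents do not support that. The intake form has a blank amount-given field for each portion, which fits weighing at least as well as copying 125. Nothing says the nominal figure is entered, and a reading of −11% would probably be noticed.

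What stands is that one column for four flavours is contradicted by the only porridge specification supplied, with no rule for choosing between them.

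**Conclusion.** The inconsistency is real and should be settled before analysis. For golden syrup portions the two sources differ by 24% of the specification value (19% of the Table 1 value) in protein and by about 3% in energy. Across all porridge portions, neither the size nor the direction of any error can be known from the documents, because the content of three flavours and the share of each flavour eaten are not given. The gap of 6.6 against 12.4 g/day shows what is at stake at full intake if either source applied to every portion; it does not estimate bias. Percentage compliance by weight and palatability are not affected by the composition mismatch.

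The control's 125 g against 125 ml is a unit conflict in the table. It would understate control compliance for unfinished bottles only if 125 served as the starting weight, and no part of the plan says it does. The 139 g bottle weight rests on summing the four main listed components.

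**What to change.** 1. Reconcile Table 1 with the manufacturer's specification for each porridge flavour offered, and append the three that are missing. If flavours differ, show a value for each.
2. Reconcile the control's 125 in the weight row with the 125 ml in its specification.
3. Add to Quantitative data analysis: ONS protein (or kcal) per portion = (1 − amount left ÷ amount given) × reconciled per-portion content for the product and flavour recorded. Define amount given as the actual net weight in grams of the full portion, weigh leftovers on the same net basis, and use the same amount given for percentage compliance.

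The cost is a few corrected cells, three added specifications, one or two sentences, and confirmation of full-portion weights. No extra patients or patient procedures are needed. The form already records flavour and grams, so existing records can be reconverted. The porridge protein figure may turn out less favourable than Table 1 suggests.

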The Strength, Assistance with walking, Rising from a chair, Climbing stairs, and Falls (SARC-F) questionnaire will be used as a measure to assess for sarcopenia [40]. It comprises five components: strength, assistance in walking, rise from a chair, climbing stairs and falls. The scores range from 0 to 10, with a score of equal to or greater than four being predictive of sarcopenia and poor outcome.

Program of Research to Integrate Services for the Maintenance of Autonomy (PRISMA-7) screening tool will be used to characterise participants' frailty status [41]. The questionnaire contains seven items with a positive score of three or more indicating frailty. The PRISMA-7 tool has been shown to have high accuracy in identifying frail older adults in the community setting [42].

Primary Outcome Measures

Primary outcome measures will include compliance to ONS and palatability.

Compliance: Compliance to ONS will be assessed by the study team via careful documentation of ONS leftovers at 2 timepoints, including after lunch (for ONS given in the morning) and early morning the following day (for ONS given after dinner), to ensure enough time for consumption. Leftovers will be weighed (g) using weighing scales (Seca Model 875 digital weighing scale) and documented by the research team. Compliance will be calculated as the percentage of the mean ONS consumed per day. Moreover, the mean intake of ONS energy (kcal/day) and protein (g/day) consumed per day will be calculated and an estimation of the percentage ingested.

Palatability: Palatability ratings, including appearance, smell, taste, sweetness, texture, thickness, aftertaste, mouth feel, and overall likability will be assessed with a 7-point hedonic Likert scale (7 = definitely like, 6 = moderately like, 5 = mildly like, 4 = neither like nor dislike, 3 = mildly dislike, 2 = moderately dislike, 1 = definitely dislike). Hedonic scales have been used to assess palatability of ONS supplements across population groups [24, 32, 43] and have good reliability [44]. Palatability ratings will be completed by participants on initial introduction of each ONS at a standardised time of day (i.e., morning ONS on day 1 and 3) (Figure 2).

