3.	In general, do you have any health problems that require you to limit your activities?		
4.	Do you need someone to help you on a regular basis?		
5.	In general, do you have any health problems that require you to stay at home?		
6.	If you need help, can you count on someone close to you?		
7.	Do you regularly use a stick, walker, or wheelchair to move about?		
	Total checked:		

SARC-F screening tool

Component	Question	Scoring
Strength	How much difficulty do you have in lifting and carrying 10lb (5 bags of sugar)?	None = 0 Some = 1 A lot or unable = 2
Assistance in walking	How much difficulty do you have walking across a room?	None = 0 Some = 1 A lot, use aids, or unable = 2
Rise from a chair	How much difficulty do you have transferring from a chair or bed?	None = 0 Some = 1 A lot or unable without help = 2
Climb stairs	How much difficulty do you have climbing a flight of 10 stairs?	None = 0 Some = 1 A lot or unable = 2
Falls	How many times have you fallen in the past year?	None = 0 1 – 3 falls = 1 ≥ 4 falls = 2
Total score		

ONS INTAKE

Date: _____ Ward: _____

ONS Product (please circle & write flavour):

Build & Restore Porridge (_____) / Fortisip (_____)

MORNING ONS

Amount given (g): _____ Amount left (g): _____

Total Intake (g): _____

Total Energy Intake (kcal): _____ Total Protein Intake (g): _____

EVENING ONS

Amount given (g): _____ Amount left (g): _____

Total Intake (g): _____

Total Energy Intake (kcal): _____ Total Protein Intake (g): _____

TOTAL ONS INTAKE

Amount given (g): _____ Amount left (g): _____

Total Intake (g): _____

Total Energy Intake (kcal): _____ Total Protein Intake (g): _____

The RELISH Study

PALATABILITY

Date: _____ Ward: _____

ONS Product (please circle & write flavour):

Build & Restore Porridge (_____) / Fortisip Compact (_____)

Look at the product. Note: Do not taste yet! Please, answer the following question (circle):
 Based on the sample appearance how much do you expect to like the taste of this product?

Definitely Like	Moderately Like	Mildly Like	Neither Like nor Dislike	Mildly Dislike	Moderately Dislike	Definitely Dislike
-----------------	-----------------	-------------	--------------------------	----------------	--------------------	--------------------

Smell the product. Note: Do not taste yet! Please, answer the following question (circle):
 Based on the sample smell, how much do you expect to like the taste of this product?

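### Any weight the porridge loses while it stands would be scored as intake, and the plan neither limits nor measures that loss

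*Combined protocol and SAP*

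**What the plan says.** Section 3, Primary Outcome Measures, names compliance and palatability as primary without ranking them. For compliance: "Leftovers will be weighed (g) using weighing scales (Seca Model 875 digital weighing scale) and documented by the research team". The morning serving is weighed after lunch and the evening serving "early morning the following day (for ONS given after dinner), to ensure enough time for consumption". The summary measure is then: "Compliance will be calculated as the percentage of the mean ONS consumed per day".

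The ONS Intake form in the data collection booklet has blanks, for each morning and evening serving, for grams given, grams left, total intake in grams, and the resulting kcal and protein. Intake is therefore a difference of two weights.

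Section 3, Intervention, describes the two products. The porridge "is powdered and mixed with 100 ml boiling water in a carton", prepared by ward staff. For the control, "Participants will be offered the ONS in a screw-topped plastic bottle". Table 1 gives serving weights of 157 g for the porridge and 125 g for the drink.

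The protocol mentions no cover for the carton, no re-capping of opened bottles on the ward, no unserved reference portion, no allowance for water loss and no container tare. It does not say whether the amount given is weighed at serving or taken from Table 1. One of the appended scientific peer reviews asked how leftovers would be measured in a standardised way. The protocol specifies weighing, but not these details.

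**The concern.** When intake is grams given minus grams left, anything that makes the leftovers lighter counts as food eaten. The plan deliberately leaves hours between serving and weighing, overnight for the evening serving. One product starts near boiling, with 100 g of added water in a 157 g portion. The other is in a bottle that can be closed.

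If the porridge loses water in that time and the drink loses less, porridge compliance is overstated relative to the drink. The error belongs to the product. It therefore enters every patient's paired difference with the same sign, whichever sequence they were allocated to, and more patients do not average it away. It falls on portions with leftovers, so it lifts the poorest eaters most. Section 2.2 says the findings will inform suitability for use at the hospital, a wider regional roll-out and the sample size of a later trial, so an error in one direction matters even in an exploratory study.

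A second gap is the starting weight. If it is nominal, both products can be mis-scored, for reasons unrelated to water loss.

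**Working it through.** **Inputs from the protocol**
- Porridge portion: 57 g powder + 100 g water = 157 g (product specification). This reproduces Table 1.
- Drink: 125 g in Table 1; the specification is per 125 ml.
- Compliance bands: low ≤30%, medium 31-79%, high ≥80% (Section 3, Data Analysis).
- Pilot (Section 6.4): of 9 patients, 3 ate the whole portion, 3 ate half and 3 ate less than half. So 6 of 9 (0.67) left half or more.
- N = 50, paired two-sided t-test (Section 5.2.1). Effect size, SD, alpha and power are not stated, so 50 cannot be reproduced.

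**Assumptions**
- Water lost per standing portion: 2, 5 or 10 g.
- Matching loss from the drink: taken as nil for the arithmetic.
- Alpha 0.05; SD of the paired compliance differences 20 to 40 points.

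**1. One portion with leftovers.** False compliance = 100 × loss / 157, so 1.57 g is 1 point.

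| Loss | Added to that portion | Mean shift if 0.67 of portions leave something |
|---|---|---|
| 2 g | 100 × 2/157 = 1.3 points | 0.9 points |
| 5 g | 100 × 5/157 = 3.2 points | 2.1 points |
| 10 g | 100 × 10/157 = 6.4 points | 4.3 points |

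A 10 g loss also credits about 230 × 10/157 = 14.6 kcal and 15 × 10/157 = 0.96 g protein (Table 1 contents) that were not eaten.

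**2. Effect on the test.** With no true difference, the noncentrality is (shift/SD) × √50. For a 2-point shift and SD 20 it is 0.10 × 7.07 = 0.71.

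| Mean shift | Two-sided rejection rate, SD 40 down to 20 |
|---|---|
| 1 point | 5-6% |
| 2 points | 6-11% |
| 3 points | 8-18% |
| 5 points | 14-41% |

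For scale, 50 complete pairs give 80% power for a standardised difference of 0.40, which is about 8 points at SD 20 and 16 points at SD 40.

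**3. Effect on the bands.** A loss of 5 × 1.57 = 7.85 g adds 5 points to the portions it affects. If it applied to all of a patient's porridge portions, a true 26-30% would move from low to medium.

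**4. Nominal starting weight, drink.** Water, protein, carbohydrate and fat per 125 ml total 78 + 18.3 + 31.4 + 12 = 139.7 g. With 125 g as the amount given and net leftovers weighed:
- untouched drink: (125 − 139.7)/125 = −11.8%
- true 67% (the hospital mean cited in Section 1): left = 0.33 × 139.7 = 46.1 g; (125 − 46.1)/125 = 63.1%

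**5. Nominal starting weight, porridge.** Take half eaten and 20 ml too much or too little water (an assumed error), scored against 157 g:
- 177 g made, 88.5 g left: (157 − 88.5)/157 = 43.6%
- 137 g made, 68.5 g left: (157 − 68.5)/157 = 56.4%

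With true weights, (given − left)/given is 50% both times.

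**The case against.** The strongest objection is that no loss is shown. The protocol names the containers but does not say that cartons stand open or that opened bottles are re-capped. The advice to close an opened bottle is the manufacturer's storage instruction, not a ward procedure. A reader might infer that porridge does lose water and the drink does not. The documents support only the conditional: whatever is lost will be scored as eaten. At 2 g the mean shift is under 1 point and the test is barely affected. Portions finished promptly carry almost no such error after serving. All of this stands, and it limits the point to an uncontrolled error of unknown size.

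Other stronger readings also fail:
- **A shift of 6 points or more in the outcome.** The 6.4 points for a 10 g loss apply to a portion with leftovers, not to the average.
- **That starting weights are not taken.** The form has a blank for grams given at every serving, which suggests weighing may be intended. The protocol does not say so.
- **That filling error favours porridge.** It goes either way, as step 5 shows.
- **That energy is inflated by a fixed kcal per gram.** No conversion method is specified.
- **That the named scale is too coarse.** Its graduation is not given.
- **That this undermines the main primary outcome.** Compliance is one of two unranked primary outcomes, and palatability ratings are not affected.

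The objection does not remove the structural fact. Intake is a delayed weight difference, the containers differ, and nothing planned would show whether the error is 1 point or 4.

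**Conclusion.** The point holds in conditional form. As written, the plan would score any water the porridge loses before weighing as porridge eaten. The loss is probably smaller for a screw-topped bottle, so the error would favour the porridge, and the crossover would not cancel it.

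Under the assumed 2 to 10 g, the average shift is about 0.9 to 4.3 points. That runs from negligible to enough to raise the false-positive rate noticeably if paired differences vary little. These figures rest on the assumed loss, no matching loss from the drink, and a leftover share taken from nine pilot patients.

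The case for weighing at serving needs no evaporation assumption. Table 1's 125 g for the drink appears to be 125 ml, and using it as the amount given would understate drink intake, again in the porridge's favour. Whether it would be used that way is not stated.

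This is a cheap improvement, not a flaw that invalidates the comparison. It is best made before data collection, because the loss cannot be recovered afterwards.

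**What to change.** 1. Weigh each filled container of both products at serving and the same container at collection, with tare recorded. Compute compliance as (given − left)/given. State this in Section 3 and correct the unit of the drink's weight in Table 1.
2. Keep the porridge covered whenever it is not being eaten, and re-cap opened bottles until weighed.
3. Weigh a few untouched portions of each product on the ward at the actual collection times and report the loss. Use it in a sensitivity analysis, with morning and overnight servings shown separately. Do not subtract it as a flat correction from partly eaten portions, because loss may depend on how much is left and for how long.
4. Calculate energy and protein as fraction eaten times content per portion. This removes the effect of extra or missing water at filling; steps 2 and 3 deal with water lost later.
5. Confirm that the scale's graduation is fine enough for portions of 125 to 157 g.

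The cost is a few seconds per serving, lids, a one-off bench check, an extra line on the intake form and, if step 5 fails, a finer scale.
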